We will use portable spirometers and FeNO machines to measure the teen's pulmonary function and airway inflammation. Some teens may have difficulty with these procedures; we will only include data for teens able to perform the procedures accurately. We will use a portable scale and stadiometer to take objective measurements for height and weight.

Exposure to Secondhand Smoke will be assessed by both interview survey and cotinine measurements. A member of the research team will collect salivary fluid samples from each child using a small sterile swab. Collection will be made according to a standard protocol developed for use with children and adolescents. Salivary samples will be stored frozen and shipped via courier to Salimetrics, LLC in State College, PA for analysis. The Environmental Assessment will include a survey inquiring about environmental exposures and an observation checklist that a member of the study team will perform.

3. Randomization

Following the baseline assessment, each teen will be randomly assigned to one of 3 groups: 1) the SB-ACT program, which includes a trial of DOT plus a self-management MI counseling intervention; 2) DOT-only; or 3) an asthma education (AE) comparison group. *Randomization will be stratified by school and preventive medication at baseline.* Since enrollment will occur over a period of 1-5 months at the start of the school year, a permuted block design will be used to assure approximately equal allocation of teens in each group over time. The randomization scheme will be independently developed by a programmer in the Biostatistics Center. After baseline completion, the interviewer will call the study coordinator who will provide the subject's ID number and treatment assignment.

4. SB-ACT Intervention:

School Nurse Assisted Preventive Medication Use (Directly Observed Therapy)

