We will communicate with the child's healthcare provider about the child's symptoms and if child is not already taking a preventive medication, to determine an appropriate preventive medication for the teen. We will facilitate the child receiving their preventive medication at school. If needed, new prescriptions will be sent to pharmacies for parent pick-up or delivery (several local pharmacies provide delivery services) with instructions indicating one canister of preventive medication to be dispensed for the home and a second canister for the teen's school. This system has been successfully implemented in our prior studies. The school nurse and teen will meet at the beginning of the program to develop an individualized plan for the timing of DOT in the school to avoid disruption of classes and allow the teen choice in this process. For the first 6-8 weeks after enrollment the teen will visit the school nurse once a day to receive a daily dose of preventive asthma medication. Study personnel will review the DOT protocol and proper administration technique with the school nurse. The purpose of this intervention component is for teens to establish a relationship with the school nurse, learn proper medication technique, and experience potential benefits of consistent

preventive therapy. As in our prior studies, most teens will receive once daily dosing since it is effective and allows for administration of medication during school hours; if more frequent dosing is needed additional doses will be taken at home. The teen will use his/her home inhaler for doses on weekend days and other days in which he/she does not attend school.

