We will notify the teen's healthcare provider that teens in the AE group have persistent asthma symptoms that warrant use of effective guideline-based preventive medications. We also will provide an in-school asthma education program,¹⁵ provided by community asthma educators or nurses. The program will include asthma management instruction and will be geared toward teens living in underserved neighborhoods. The program will match the time and attention of the MI counseling portion of SB-ACT. Sessions will be delivered at school by a trained health educator, in a similar structure and time-schedule to the MI intervention (i.e., each teen will receive three 1-on-1 educational sessions at school). Sessions will cover 3 main topics: 1) lung physiology and asthma basics, 2) triggers, symptoms, and warning signs, and 3) medications and self-advocacy. As in SB-ACT, caregivers will be called after each session to reinforce key points and answer questions. Bi-monthly supervision will be provided by the PI and research coordinator to assure fidelity to the AE intervention; all sessions will be audiotaped and 20% will be reviewed.

Teens will not be blinded to group allocation; they will be told they are randomly assigned to different ways of approaching asthma management. As in our prior work, to avoid differential attrition we assure sessions are interactive and provide flexible scheduling and reminders.

7. Asthma Control Status at Follow-Up

Criteria for a preventive medication adjustment recommendation at the 3 month Follow-Up assessment for the DOT-only and SB-ACT treatment groups:

1. Caregiver 3mo. FU; *one (or both) below evidencing poor control status*:

- a. NHLBI criteria
- b. ACT score \leq 19

AND

2. Teen 3mo. FU; *one (or both) below evidencing poor control status*:

- a. NHLBI criteria
- b. ACT score \leq 19

AND

3. Caregiver and/or teen reports making any effort to take/continue the prescribed preventive medication at school/home

If the above conditions hold true, a step-up adjustment recommendation (and/or a change to once daily dosing) will be made. This will happen regardless of whether school DOT is continuing or the teen has already transitioned to independent use.

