Medication Adjustment Procedure: Generate a NHLBI symptom report to justify a preventive medication action and draft a prescription recommendation for PCP to consider and authorize (possibly with edits). After receipt of PCP decision, caregiver will be contacted to explain recommendation and obtain consent. Submit new prescription to pharmacy and deliver

to school/home as needed. If medication adjustment is NOT agreed to by caregiver then notify PCP of decision not to adjust.

Note: If caregiver and teen both report NO attempt to be adherent and asthma control is poor then Asthma Care Coordinator will encourage caregiver/teen to restart the previously prescribed preventive medication and no adjustment recommendation will be initiated.

For AE-only subjects who meet the criteria above: Send caregiver a poor control follow-up notification letter encouraging family to pursue preventive asthma care due to teen's continuing persistent symptoms. Send PCP a notification letter calling attention to teen's continuing persistent symptoms.

8. Participant Follow-up

Outcome measures will be assessed at 3, 5, 7 and 12 months after baseline for all subjects by an independent group blinded to treatment allocation. We will use structured telephone interviews with both the teen and caregiver for follow-up surveys. We may also send reminders and schedule appointments through text messages and emails. Text messages will be formatted in a manner that provides research relevance in the absence of personal health information (PHI). We may use a limited data set when sending text messages that can include dates and times for visits or telephone call reminders. FeNO, spirometry, cotinine, height, weight and adherence measurements will be conducted through home or school visits at specific time-points (see below). Medical record review also will be performed.

Measures (see below for Measurement Table with scales and timing of administration)

Symptom Severity:

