This is **not** a drug investigational study since the effectiveness and safety of the drugs are not being tested. The randomized trial proposed will pose minimal risk to the teens, since the medications used by the teens (and delivered at school for the teens in the SB-ACT and DOT-only groups) are FDA approved preventive medications that are recommended as the standard of care⁴⁵ for children and adolescents with the degree of symptom severity required for enrollment into the program. The most common side effects of inhaled corticosteroids, including yeast infection of the mouth and facial rash, will be assessed during each follow-up interview. Any significant concerns will be relayed promptly to the study coordinator, the principal investigator, the teen's health care provider, the Institutional Review Board, the DSMB and the NIH. There is a potential risk of adverse effects on linear growth from the use of inhaled steroids;⁴⁶ however, this risk is felt to be outweighed by the benefits for children and adolescents with persistent asthma. In general, these medications are well tolerated and safe. Health care providers will prescribe all medications and will follow the teen for any potential side effects and monitor the teen's growth during the course of the study.

The frequency and severity of all reported adverse events will be systematically recorded. Telephone interviewers will inquire about any adverse events, and specifically ask about any yeast infections of the mouth and facial rash. Any teen experiencing an acute asthma exacerbation at the time of a home visit or follow-up phone call will be referred immediately to their health care provider for care, and their caregiver will be notified. In addition, school nurses will be instructed to contact the caregiver of any teen presenting to the nurses office with acute symptoms and refer them promptly to their health care provider.

There is a risk that the study team may discover an unknown medical condition. If this is to occur, we will refer the family to their health care provider or another appropriate health care professional for evaluation and treatment.

Data Safety Monitoring Plan (DSMP):

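### As written, the 3-month poor-control letters in the AE group miss teens with no preventive prescription or no reported effort to take one

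*Combined protocol and SAP*

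**What the plan says.** Section C.7 (Asthma Control Status at Follow-Up) opens with a list headed "Criteria for a preventive medication adjustment recommendation at the 3 month Follow-Up assessment for the DOT-only and SB-ACT treatment groups". The list has three items joined by AND. Items 1 and 2 are poor control by caregiver report and by teen report, each judged on NHLBI criteria, an ACT score of 19 or less, or both. Item 3 is "Caregiver and/or teen reports making any effort to take/continue the prescribed preventive medication at school/home".

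After the adjustment procedure comes a Note for the case where control is poor and neither reporter describes an attempt at adherence. The coordinator will then "encourage caregiver/teen to restart the previously prescribed preventive medication and no adjustment recommendation will be initiated".

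The AE instruction follows: "For AE-only subjects who meet the criteria above: Send caregiver a poor control follow-up notification letter encouraging family to pursue preventive asthma care". Its next sentence sends the provider a letter about the teen's continuing symptoms, on the same trigger. Nothing exempts AE from item 3.

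Four other parts of the protocol bear on who could be left out:

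- **Section B:** eligibility does not require a preventive prescription.
- **Section C.3:** "Randomization will be stratified by school and preventive medication at baseline".
- **Section C.4:** in SB-ACT the study contacts the provider, "if child is not already taking a preventive medication, to determine an appropriate preventive medication for the teen". Section C.5 makes a matching commitment for DOT-only.
- **Section C.6:** for AE, the provider is told that "teens in the AE group have persistent asthma symptoms that warrant use of effective guideline-based preventive medications". No study help in obtaining a prescription is described.

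**The concern.** Item 3 makes sense for a step-up, because a dose should not be raised in a teen who is not taking the current one. AE offers no step-up. Its caregiver letter exists to move a family towards preventive treatment. Carrying item 3 over reverses the targeting: families already making some effort get the letter, and families making none, or with nothing prescribed, do not.

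What is at stake is one message at one time point, namely telling the family and the provider that both reports showed poor control at 3 months. The teens who miss it are those still untreated after the general provider notice. This is a modest patient-care matter. It does not threaten the validity of the primary comparison.

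**Working it through.** The plan gives no figure to reproduce here, so the check is of the trigger's logic.

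**Trigger as written.** Let C1 be poor control by caregiver report, C2 poor control by teen report, and C3 any effort to take the prescribed preventive, reported by at least one of the two. Both AE letters are sent if and only if C1 AND C2 AND C3.

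**Cases with C1 and C2 both true:**

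| AE teen at 3 months | C3 | Caregiver letter | Provider letter |
|---|---|---|---|
| Preventive prescribed, effort reported by caregiver, teen or both | true | sent | sent |
| Preventive prescribed, no effort reported by either | false | not sent | not sent |
| No preventive prescribed | cannot be met as worded | not sent | not sent |

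One reporter describing any effort satisfies C3. It is therefore a low bar, and partial users still trigger both letters.

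**Is the third row a real group?** Baseline preventive medication is a stratification factor and is not an entry requirement, so teens without one are expected in every arm. Study help to obtain a prescription is described for SB-ACT and DOT-only only. An AE teen without a prescription gets one only if the provider acts on the notice or the family seeks it.

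**Does another provision deliver the same message?**

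- *The Note in C.7.* It names no arm, so it may or may not cover AE. If it does, it offers encouragement to restart an earlier prescription. It sends no provider letter and does not fit a teen who was never prescribed one.
- *The general provider notice in C.6.* It concerns the persistent symptoms of AE teens in general and is separate from the 3-month letters.
- *The AE sessions and caregiver calls in C.6.* They follow a schedule similar to the MI sessions in C.4, which start at 4 to 6 weeks and end 6 weeks later: 4 + 6 = 10 to 6 + 6 = 12 weeks. They would be finished or nearly so by the 3-month assessment, and nothing ties them to its result.
- *Acute referral in C.13.* "Any teen experiencing an acute asthma exacerbation at the time of a home visit or follow-up phone call will be referred immediately". This covers acute exacerbations, not ongoing poor control.

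**Scale.** Inputs are 430 teens in three groups recruited over 4 years (Section B).

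- AE group: 430 / 3 = 143 teens.
- Each 1% of AE with C1 and C2 true but C3 false: 0.01 × 143 = 1.4 teens.
- Ceiling on all AE letters, if every AE teen qualified: 143 × 2 = 286.
- Per recruitment year: 286 / 4 = about 72.

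The documents give no rates of prescription or reported effort in AE at 3 months, and none is assumed. The 1.4 is therefore a unit conversion and not an estimate. The 286 bounds all AE letters, so the increment due to the fix can only be smaller or equal.

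**The case against.** The best counter-argument is that the back-reference is only loosely worded. Item 3 is phrased for arms with school dosing, items 1 and 2 are the ones that define poor control, and the AE document is described as a poor-control letter. On a purposive reading, AE teens who meet items 1 and 2 get it. That may be what the sponsor meant, and the documents do not show that any letter would be withheld in practice. It does not settle the matter, however. The only list labelled as criteria has three parts, and the Note shows that the protocol can state poor control separately from effort when it wants to. If items 1 and 2 were intended, the edit simply records that and keeps handling consistent across the recruitment years.

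The second argument is that little is lost. AE providers are notified, one of the three education topics covers medications and self-advocacy, caregivers are called after each session, and acute episodes are referred. All of this is true, and it is why the point is graded as an improvement and not as a serious defect.

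The third argument concerns the trade-off. If few teens are affected, the benefit is small. If many are, the extra prompts reach control families and providers before two of the three primary assessments (5 and 7 months), and the loss of contrast need not be slight. This stands as a caution, because the documents cannot size it. It does not justify the present rule: a wish to limit contact in the control arm would not explain why partial users get letters and untreated teens do not.

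**Conclusion.** The concern holds on the text as written. An AE teen with poor control on both reports triggers neither 3-month letter when no preventive is prescribed or when neither reporter describes effort. That works against the caregiver letter's own purpose.

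The size is unknown. It could be small, given the low bar of item 3, at about 1.4 teens for each 1% of an AE group of about 143 (equal allocation assumed). The conclusion rests on reading the AE sentence as referring to all three listed criteria, which is what it says. No claim is made about bias, power or comparability between arms: teens in the DOT arms with no attempt reported get no adjustment recommendation either. This is a cheap change that should be made.

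**What to change.** In the AE instruction of Section C.7, change the trigger to: *AE subjects who meet criteria 1 and 2 (poor control by both caregiver and teen report), whether or not criterion 3 is met.* Apply it to both the caregiver letter and the provider letter. Keep criterion 3 for the step-up recommendation in SB-ACT and DOT-only, where it belongs.

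Optionally, the study coordinator can log each AE letter (date, recipient, criterion 3 status), kept away from the blinded follow-up group. The wording change does not depend on this.

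The cost is a one-phrase amendment and some extra form letters, within the ceiling of 286 for the whole trial. The downside is more prompting of AE families and providers before the 5- and 7-month assessments, which may slightly narrow the contrast with SB-ACT. A log would show how much prompting occurred.

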a) The primary outcome measure will be the number of symptom-free days (SFDs) at the 3, 5, and 7 mo. follow-ups. This outcome measure is consistent with the symptom monitoring suggested by the national guidelines,¹⁶ and we collected prospective data on SFDs in our prior studies, enabling a realistic calculation of sample size requirements. At each follow-up, parents and teens will report the number of days the teen experienced no symptoms of asthma (defined as 24 hrs with no coughing, wheezing, shortness of breath, and no need for rescue medicine) in the past 2 weeks. Symptom diaries will assist with recollection.

b) Secondary measures: Parents and teens will be asked to report the number of "steroid bursts" for asthma, as well as urgent (ED visits, hospitalizations, school exacerbations requiring treatment) and non-urgent (primary and specialist care) visits. With parent permission, we can access charts at each medical practice and will review medical records to verify visits. We also will measure the number of nights with asthma symptoms, days needing rescue medications, days with limited activity, and asthma control with the asthma control test (ACT).^{17,18}

Adherence: We will use Horne's adherence scale,¹⁹ and also will ask teens to report doses missed in the prior 2 weeks. To provide objective adherence data for teens in each group, we will monitor dose counters that are integrated into medication canisters. Almost all inhaled steroids now include counters, and in our prior study 99% of children used medication that included integrated counters. At baseline, 5-months, and 7-months, we will use home visits to document the number of doses on the teens' preventive medication inhaler (or count remaining pills for oral medications, i.e.; Singulair), and return 2 weeks later to re-measure the doses used. Based on the prescribed regimen, we will calculate adherence ($\#$ actuations / $\#$ prescribed) over the prior 2 wks. For teens in the SB-ACT and DOT-only groups, we will also collect school medication administration logs and will record the time to transition to independent medicine use.

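### As written, the dose-counter adherence ratio leaves school doses out of the numerator but keeps them in the denominator for SB-ACT and DOT-only teens still on school DOT at the 5- or 7-month count

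*Combined protocol and SAP*

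**What the plan says.** All references are to the combined protocol and SAP.

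- **How the count is made (section 8, Adherence paragraph).** "At baseline, 5-months, and 7-months, we will use home visits to document the number of doses on the" teen's preventive inhaler, "and return 2 weeks later to re-measure the doses used". Then: "Based on the prescribed regimen, we will calculate adherence", as actuations over doses prescribed for the two weeks.
- **School data (same paragraph).** For SB-ACT and DOT-only, "we will also collect school medication administration logs and will record the time to transition to independent medicine use". Nothing links the logs to the ratio.
- **Where doses are taken (section 4).** "For the first 6-8 weeks after enrollment the teen will visit the school nurse once a day" for a dose. Where a new prescription is needed, it asks for "one canister of preventive medication to be dispensed for the home and a second canister for the" school. "The teen will use his/her home inhaler for doses on weekend days and other days in which he/she does not attend school". Most teens are expected to be dosed once daily; any additional doses are taken at home. Section 5 likewise provides for medication at both home and school in DOT-only.
- **How long DOT may run.** The planned trial is 6-8 weeks. Sections 4 and 5 allow a teen in either arm to ask to continue, with no limit stated. Section 7 makes its 3-month medication review apply whether or not school DOT is still running.
- **Where the count is made (opening of section 8).** A general sentence covering several measures, adherence among them, allows visits at home or at school and refers the reader onward. The paragraph that follows names home visits only. The section 9 table lists counter monitoring without a location.

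**The concern.** The numerator and denominator cover different sets of doses. The inhaler read at home records home doses; the prescribed regimen includes the school doses. For a teen who has returned to independent use the two sets coincide. For a teen still receiving school DOT they do not, and a teen who misses nothing appears largely non-adherent.

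Planned school dosing exists only in SB-ACT and DOT-only, so against AE the error can run in one direction only: it lowers apparent adherence in the DOT arms. Better adherence than AE is one of the hypotheses in the Background section, and the counter is the only adherence measure offered as objective. A real benefit could be partly hidden. SB-ACT versus DOT-only could also be distorted if continuation differs between those arms, in a direction the documents do not reveal.

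**Working it through.** The plan gives no expected value, margin or power for objective adherence, so there is no stated figure to reproduce. The check applies the section 8 ratio to one teen.

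**Inputs.** Window of 14 days (section 8). Once-daily dosing for most teens, extra doses at home, home inhaler on non-school days (section 4). Assumed: 10 school days in the window with full attendance, and every dose taken.

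**Once daily.** Prescribed = 14. Home actuations = 14 − 10 = 4. Ratio = 4/14 = 28.6%.

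**Twice daily, one dose at school.** Prescribed = 28. Home actuations = 4 × 2 + 10 × 1 = 18. Ratio = 18/28 = 64.3%.

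**Varying the number of school days on DOT in the window:**

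| School days | Once daily | Twice daily |
|---|---|---|
| 10 | 4/14 = 28.6% | 18/28 = 64.3% |
| 8 | 6/14 = 42.9% | 20/28 = 71.4% |
| 5 | 9/14 = 64.3% | 23/28 = 82.1% |
| 0 | 14/14 = 100% | 28/28 = 100% |

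With school doses added to the numerator, every cell is 100%.

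**Imperfect home use.** Take a once-daily teen with 10 school doses given and 70% adherence on the 4 home days, so 4 × 0.7 = 2.8 home doses. As written: 2.8/14 = 20.0%. Home plus school: 12.8/14 = 91.4%. Home doses over home-scheduled doses: 2.8/4 = 70%. The second figure describes total exposure and the third describes independent use; the first describes neither.

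**Who can be affected.** Five months is 5 × 30.44/7 = 21.7 weeks. DOT of 6-8 weeks from enrollment ends 21.7 − 8 = 13.7 to 21.7 − 6 = 15.7 weeks before that count. Seven months is 7 × 30.44/7 = 30.4 weeks, so the gap is 22.4 to 24.4 weeks. Only teens who extend DOT for months are still on it.

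**Calendar.** Section 1 runs enrollment from the first day of school to the end of February. An early-September enrollee has counts in about February and April. An end-of-February enrollee has them in late July and late September. A window with no school days carries no error.

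**The case against.** The formula says actuations, not home actuations. The opening of section 8 allows adherence to be measured at school, the section 9 table sets no location, and the sentence directly after the formula collects school logs in exactly the two arms concerned. The team may well intend to combine them. Most teens should have left DOT long before either follow-up count. The counter is one of three adherence measures, alongside the adherence scale and self-report (the team "also will ask teens to report doses missed in the prior 2 weeks"). Any error works against the intervention relative to AE, so it would not create a false benefit there.

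Most of this stands, and it limits the point. It does not remove it: no sentence adds school doses to the numerator or takes school-scheduled doses out of the denominator, and the only detailed procedure names home visits. Continued DOT is also foreseen, since section 7 allows for it at 3 months and section 8 records time to transition.

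Stronger readings that a reader might infer are not supported:

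- **A known bias in arm means.** The share still on school DOT at 5 or 7 months is not in the documents and could be zero. Attendance, holidays and the enrollment pattern would also matter. The per-teen figures cannot be turned into an arm-level estimate.
- **A contaminated baseline count.** This would need assignment to precede the second baseline reading, DOT to begin within those two weeks, and the count to be used as a covariate or change reference. Section 3 assigns after baseline completion without saying whether that includes the second reading, and section 16 names no adherence covariate. Only a clarification is warranted.

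**Conclusion.** The point holds as a gap in a stated formula: the ratio misfires in a situation the protocol itself permits. For an affected teen with perfect adherence and 10 school days in the window, the score is 29% (once daily) or 64% (twice daily) instead of 100%. These figures rest on full attendance and on the home inhaler alone being read. The direction against AE is known; the arm-level size is not, and may be small. The effect is nil in windows without school days. The primary symptom-free-day analysis is unaffected. This is a cheap improvement to a secondary outcome, best settled before data are analyzed so that the choice of numerator cannot depend on results.

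**What to change.** In the analysis plan, for SB-ACT and DOT-only:

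1. Define the numerator as home-counter actuations plus school-log (or school-counter) doses over the same two weeks, against all prescribed doses.
2. Report home-only adherence separately, with only home-scheduled doses in its denominator, so that nurse-observed doses are not read as independent use.
3. Report by arm the number still on school DOT at each count.
4. Merge the logs at data management, so that the assessors, whom section 8 describes as blinded, do not see them.

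Reconcile the two statements in section 8 on where adherence is measured. State whether the second baseline count comes before assignment.

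The cost is mainly wording, because the logs and time to transition are already to be collected. The downsides are that DOT-arm values then combine a device counter with a nurse record, and that log entries must be dated to match the window.
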